## 9.3.2 Power Considerations

The primary outcome is the incidence of bacteremia during the study period. Analysis will be performed separately for AL patients and HSCT patients. For children with AL or HSCT, a child will have experienced the primary endpoint once he/she experiences at least 1 episode of true bacteremia during the study period. If we assume that the risk of at least 1 episode of bacteremia in either patient cohort in the control arm (no levofloxacin) is 30% and a clinically significant reduction in bacteremia is 15% (relative risk reduction of 50%), about 133 children in each arm will provide about 84% power in detecting the treatment effect on the incidence of bacteremia (30% in control without levofloxacin vs. 15% in treatment with levofloxacin). The test considered is a 2-sided Chi-square test with alpha level of 0.05. Therefore, in the original version of the protocol we proposed to enroll 532 eligible and evaluable children in total: 266 AL patients and 266 HSCT patients. Based on interim data released by DSMC in fall 2013, the recently observed rate of bacteremia in HSCT control arm is 22-25%. Given such observed rate of bacteremia being closer to 20% rather than 30% for HSCT control arm, to ensure adequate power for studying the effect of levofloxacin, in Amendment #3 we increased the planned sample size of HSCT patients to 400 eligible and evaluable patients (200 per arm), which will provide 80% power for detecting a 10% difference in bacteremia rate (20% in control arm vs. 10% in treatment arm) for HSCT patients. For AL patients, the sample size remains 266 patients. This sample size gives 84% power for a 15% reduction in bacteremia rate when the bacteremia rate for AL control arm is 30% (30% vs. 15%); the power is at least 80% for a 17.5% reduction in bacteremia rate when the bacteremia rate for AL control arm is 40-60% (control vs. treatment being 40% vs. 22.5%, or 50% vs. 32.5%, or 60% vs. 42.5%).

For the secondary endpoint on total number of days of antibiotic administration, considering a 2-sample t-test, with about 133 AL patients per arm we will have 90% power to detect a difference of 0.4 SD between the 2 arms in the mean of the number of days of parenteral antibiotic administration at 2-sided alpha of 0.05; with about 200 HSCT patients per arm we will have 85% power to detect a difference of 0.3 SD between the 2 arms in the mean number of days of parenteral antibiotic administration. For the secondary endpoints on the incidence of febrile neutropenia, severe infection, and death from bacteremia, the observed incidence rate will be compared between the 2 randomized arms. The power of such secondary analyses depends on the baseline incidence and the difference in incidence between the 2 arms. For these secondary analyses, if, for example, we consider possible baseline incidence values of 40%, 30%, 20%, 15%, 10%, or 5% in the control arm, in AL group (about 133 patients per arm) we will have a power of 95%, 84%, 63%, 49%, 34%, or 19%, respectively, to detect a levofloxacin treatment effect if levofloxacin leads to a relative reduction of 50% in the corresponding baseline incidence rate (i.e., rate with levofloxacin of 20%, 15%, 10%, 7.5%, 5%, or 2.5% respectively); for HSCT group (about 200 patients per arm), the corresponding power for a 50% relative reduction in these baseline incidence rates will be 99%, 95%, 80%, 66%, 48%, and 26% respectively. The test considered is a Chi-square test with 2-sided alpha of 0.05. It can be seen that the power for detecting a treatment difference in these secondary analyses might be limited if the baseline incidence is rare.

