## 9.3.4 Interim Monitoring

Interim efficacy monitoring on the incidence of bacteremia will be performed twice when data is available for approximately one-third and two-thirds of patients (separately for AL patients and HSCT patients). Monitoring boundary will be based on Lan-Demet's method with spending function  $\alpha t^2$ . Futility analyses based on conditional power will also be performed at the same time separately for each patient group. The probability of establishing efficacy of levofloxacin given the currently observed data will be calculated. In calculating the conditional power, the outcome for future patients will be assumed to follow the alternative hypothesis. If the conditional power falls below 10%, it will be considered evidence that it is unlikely to establish efficacy of levofloxacin in the particular patient group at the end of the study. The data will be referred to the COG Data Safety and Monitoring Committee (DSMC) for consideration of early termination for the particular patient group. Accrual will not be suspended for these interim monitoring and analyses. The incidence of musculoskeletal disorder will be monitored between the 2 arms by descriptive statistics and Fisher's exact test at each interim DSMC report, which occurs approximately every 6 months during the first 2 years and annually thereafter. For tendon rupture, as concurrent steroid use is considered a risk factor, the analysis will also be considered separately for levofloxacin patients with/without concurrent steroid use or with adjustment for steroid use. A previous report on > 2,500 patients found a small increase in the musculoskeletal disorder incidence (3.4% versus

1.8%) in levofloxacin treated patients; however our study is not powered to detect a difference of this magnitude. Therefore, the monitoring on incidence of musculoskeletal disorder will be informal and mainly for safety reassurance. Such safety monitoring will always be done at marginal alpha level of 0.05 and not adjusted for the multiple comparisons. If any such safety comparison suggests a significantly higher incidence of musculoskeletal disorder for levofloxacin, the study committee will carry out a review of the observed disorders; the results and any committee recommendation will be reported to the DSMC. The DSMC may also have its own assessment and recommendation about musculoskeletal event safety given the observed data.

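### The 80% (HSCT) and 84% (AL) powers in 9.3.2 are single-look figures; with the two efficacy looks of 9.3.4 they are about 78% and 82%, and the final test level is not stated

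*Combined protocol and SAP*

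**What the plan says.** Section 9.3.2 sizes each cohort on one comparison of bacteremia incidence: "The test considered is a 2-sided Chi-square test with alpha level of 0.05". For AL, "about 133 children in each arm will provide about 84% power in detecting the treatment effect on the incidence of bacteremia", at 30% against 15%. For HSCT, Amendment #3 raised the target to 400 evaluable patients, 200 in each arm, a number "which will provide 80% power for detecting a 10% difference in bacteremia rate", with the control rate set at 20% and the levofloxacin rate at 10%. The reason given is that "the recently observed rate of bacteremia in HSCT control arm is 22-25"%, which the section regards as nearer 20% than 30%. For AL it also claims at least 80% power for a 17.5-point reduction from control rates of 40% to 60%.

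Section 9.3.3 names the chi-square test for the final comparison within each cohort and gives no significance level.

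Section 9.3.4 plans two interim efficacy analyses per cohort, at roughly one-third and two-thirds of patients: "Monitoring boundary will be based on Lan-Demet's method with spending function" αt². It gives no numerical total alpha. It adds a futility rule: conditional power under the alternative of less than 10% is referred to the DSMC.

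No section gives the final nominal level, the power under the sequential design, or any allowance for the looks in the sample size.

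**The concern.** An αt² spending function uses a substantial part of the alpha before the end, so the final test must be stricter than 0.05. The power section is written as if it were not. The 80% is the stated basis for enlarging the HSCT cohort to 400, so it should describe the design that will be run.

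The second gap is practical. The only level printed for the primary chi-square test is the 0.05 of the power calculation. A final p-value between about 0.039 and 0.05 would then be open to dispute: a reader of 9.3.2 might call it significant, while the 9.3.4 boundary would not.

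**Working it through.** **Inputs.** From 9.3.2: 200 per arm, 20% vs 10% (HSCT); 133 per arm, 30% vs 15% (AL); two-sided 0.05. From 9.3.4: looks at t = 1/3 and 2/3, spending αt². Assumed: the total α is the 0.05 of 9.3.2, and the looks fall exactly at those fractions.

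**Step 1: reproduce the stated power (one look, pooled variance, no continuity correction).**

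Power = Φ{[(p₁ − p₂) − 1.96·s₀]/s₁}, where s₀ = √[2p̄(1 − p̄)/n] and s₁ = √{[p₁(1 − p₁) + p₂(1 − p₂)]/n}.

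- HSCT: s₀ = 0.03571, s₁ = 0.03536; (0.10 − 1.96 × 0.03571)/0.03536 = 0.849; Φ = 80.2%.
- AL: s₀ = 0.05121, s₁ = 0.05037; (0.15 − 1.96 × 0.05121)/0.05037 = 0.985; Φ = 83.8%.

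Both match the plan. Section 9.3.2 also lists the same 80% and 84% for secondary endpoints with these baseline rates, for which no efficacy looks are planned. The primary figures are therefore single-look powers.

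**Step 2: boundaries.** Cumulative alpha is 0.05 × 1/9 = 0.0056, 0.05 × 4/9 = 0.0222, then 0.05. Solving recursively on the Brownian-motion scale:

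| Look (t) | Cumulative alpha | Critical \|Z\| | Nominal two-sided p |
|---|---|---|---|
| 1/3 | 0.0056 | 2.77 | 0.0056 |
| 2/3 | 0.0222 | 2.35 | 0.0189 |
| 1 | 0.0500 | 2.06 | 0.0392 |

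Spending 0.025t² one-sided gives the same boundaries.

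**Step 3: overall power.** The drift is set to the fixed-sample power (0.849 + 1.960 = 2.809 for HSCT; 0.985 + 1.960 = 2.945 for AL), and crossing probabilities are summed over the three looks.

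| Scenario | One look at 0.05 | With planned looks |
|---|---|---|
| HSCT 20 vs 10 | 80.2% | 78.4% (0.125 + 0.363 + 0.297, rounded) |
| AL 30 vs 15 | 83.8% | 82.2% (0.142 + 0.390 + 0.290) |
| AL 40 vs 22.5 | 87.3% | 85.9% |
| AL 50 vs 32.5 | 83.0% | 81.4% |
| AL 60 vs 42.5 | 81.8% | 80.2% |

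Binomial simulation (1,000,000 trials per scenario) gives 78.9% for HSCT 20 vs 10 and 82.5% for AL 30 vs 15. If the 10% conditional-power rule always stopped a cohort, simulated power would be 78.8% and 82.4%, so futility adds almost nothing.

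**Step 4: sensitivity to look timing.** The HSCT target moved from 266 to 400 after interim data, and actual look times are not given. As an illustrative assumption, if both HSCT looks were timed to 266 patients, t = 88.7/400 = 0.22 and 177.3/400 = 0.44. The final level is then 0.044 and power 79.2%.

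**Step 5: final test at 0.05.** Keeping the two interim boundaries and using |Z| = 1.96 at the end gives a type I error of 0.0595 per cohort (looks at 1/3 and 2/3).

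**Step 6: HSCT at the observed control rate, 200 per arm.**

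| Control rate | Effect | One look | With looks |
|---|---|---|---|
| 22% | 10 points | 76.1% | 74.2% |
| 25% | 10 points | 70.7% | 68.6% |
| 22% | halved | 84.5% | 82.9% |
| 25% | halved | 89.6% | 88.4% |

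**The case against.** The best defence is that nothing in 9.3.2 is miscalculated and the loss is immaterial. It is 1.6 to 1.8 points at the planned looks and about 1.0 point for HSCT if both looks were timed to 266. The choice of normal approximation or binomial calculation moves the HSCT figure by about half as much as the looks do (simulated single-look power is 81.1%, against 80.2%). The section itself uses approximate figures for AL, and the assumed control rate matters far more. All of this stands: the stated powers are incomplete, not wrong for the test they name.

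A reader might infer that type I error is inflated. The documents do not support that. An overall 0.05 is compatible with Lan-DeMets spending, because αt² reaches α at t = 1 and so determines the final boundary. The 5.9% arises only if that boundary is set aside, and no section says it will be. What remains is that the final level is nowhere written down.

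A reader might also infer that HSCT is badly underpowered at the observed 22% to 25%. That follows only if the target is a fixed 10-point difference, which is how 9.3.2 words it. The same section defines the original target as a 50% relative reduction, 20 vs 10 is also a halving, and the secondary power figures use halving throughout. On that reading power is 83% to 88% with the looks. Neither reading should be given alone.

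**Conclusion.** The point holds in a limited form. The 80% and 84% are single-look powers that leave out the looks in 9.3.4. Under the planned monitoring they are about 78% and 82%, with a final nominal level of about 0.039. HSCT falls just below 80%; about 208 evaluable patients per arm instead of 200 would restore it. The AL claim of at least 80% for control rates of 40% to 60% still holds, narrowly at 60%.

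These figures assume a total two-sided alpha of 0.05 per cohort and looks at exactly one-third and two-thirds. With both HSCT looks timed to 266 they become about 0.044 and 79%. The shortfall does not call the design into question. The more useful correction is to state the final level in advance.

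**What to change.** Wording only, with no added patients.

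- **Section 9.3.2:** restate primary power under the 9.3.4 boundaries, about 78% (HSCT, 20 vs 10) and 82% (AL, 30 vs 15), and state the look times assumed. If HSCT power at the observed 22% to 25% control rate is added, give both readings: 74% to 69% for a 10-point difference and 83% to 88% for a 50% relative reduction.
- **Section 9.3.3:** state that 0.05 two-sided is the overall level in each cohort, and that the final chi-square test uses the Lan-DeMets final boundary recomputed at the actual information fractions (about 0.039 for looks at one-third and two-thirds). For HSCT, the fractions should reflect when the looks were actually taken relative to 400.

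The cost is a slightly less favourable stated power.

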## 9.3.3 Analysis Plans

All primary analyses will be performed separately for AL and HSCT patients, and all primary analyses involving treatment effect will be intent-to-treat (ITT).

The primary outcome is the incidence of bacteremia during the study period. Within either patient cohort, we will compare the incidence of the bacteremia between the 2 randomized arms using the Chi-square test. If within either patient group the data suggest a possible difference in baseline incidence between the

2 randomization strata, we will consider Cochran-Mantel-Haenszel test to examine the association between the incidence of bacteremia and the study treatment with adjustment for the randomization strata; Breslow-Day test for homogeneity in odds ratio across the strata will also be considered. Logistic regression models will be performed to evaluate the treatment effect on the incidence of bacteremia adjusting for stratification and other baseline patient characteristics. Logistic regression models combining AL and HSCT patients will also be performed to evaluate the effect of levofloxacin on bacteremia in the two patient groups, and a test for interaction between treatment and patient group will be performed to examine if treatment effect differs between the two patient groups.

For the secondary endpoints, the total number of days of parenteral antibiotic administration will be compared between the 2 arms using 2-sample t-test. Wilcoxon rank sum test will also be considered. We will also use linear regression models to estimate any treatment difference in total days of parenteral antibiotic administration and adjust for randomization stratification and potentially other patient or treatment characteristics. The incidence of febrile neutropenia, severe infection from bacteremia, fatal infections from bacteremia and musculoskeletal adverse events will be compared between the 2 randomized arms similarly as the analyses on bacteremia. For the analysis on the incidence of tendon rupture, we will also consider separating levofloxacin patients into those with/without concurrent steroid use and comparing them separately to control patients, or adjusting for concurrent steroid use as covariate in logistic regression models. The incidence of CDAD and proven or probable IFIs will also be compared between the 2 study arms in a similar manner. A patient with multiple documented episodes of CDAD or proven or probable IFI will only be counted once when calculating the binary incidence rates. For these secondary endpoints, appropriate regression models that combine AL and HSCT patients will be performed to evaluate the treatment effect with levofloxacin in the two patient groups; test for interaction between treatment and patient group will be performed to examine if the effect of levofloxacin on these secondary endpoints differs between the two patient groups.

Factors that can potentially confound the true association of the randomized exposure (levofloxacin) with the primary and two of the secondary outcome measures (1.2.1 and 1.2.2) will be compared across the two randomization arms to assure a balanced distribution. These include the use of antibiotic or ethanol as dwells or locks in central venous catheters (CVC) to reduce CVC infections and the use of chlorhexidine gluconate baths to reduce CVC infections. Analyses adjusting for these factors will be exploratory in nature.

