#### 3.1.6 Randomization

Randomization will take place at the time a patient is enrolled on study via eRDES. Patients will be assigned to either levofloxacin treatment or no levofloxacin treatment. Randomization will be stratified by

diagnosis/therapy: 1) those with *de novo*, secondary or relapsed AML or acute leukemia of ambiguous lineage treated with standard AML therapy; 2) those with relapsed ALL; 3) those undergoing autologous HSCT; 4) those undergoing allogeneic HSCT.

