#### 9.0 STATISTICAL CONSIDERATIONS

## 9.1 Statistical Design

This study is a randomized trial to investigate the effect of levofloxacin on preventing bacteremia in children being treated for AL or undergoing HSCT. Patients will be randomized between levofloxacin and no levofloxacin during 2 consecutive cycles of chemotherapy for AL or during 1 HSCT. Randomization will be stratified by 4 groups: 1) *de novo*, secondary or relapsed AML or acute leukemia of ambiguous lineage treated with standard AML therapy; 2) relapsed ALL; 3) autologous stem cell transplantation; 4) allogeneic stem cell transplantation. The study is designed to analyze AL and HSCT patients separately.

The primary aim is to determine the effect of levofloxacin on the incidence of bacteremia during the study timeframe of 2 cycles of chemotherapy or 1 transplant procedure among AL and HSCT subjects respectively. Besides assessing the safety of levofloxacin, especially on musculoskeletal disorders, other secondary aims are to determine the effect of levofloxacin on: total days of antibiotic administration, incidence of fever with neutropenia, incidence of severe infection, incidence of death from bacterial infection, incidence of CDAD, incidence of IFI, resistance patterns of bacterial isolates from sterile site cultures, evolution of antimicrobial resistance from stool or peri-rectal swab isolates of *E. coli, K. pneumoniae, P. aeruginosa* and S. *mitis* and presence of stool colonization by carbapenem-resistant Enterobacteriaceae.

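### Randomization is stratified by two groups in each cohort, but the primary bacteremia test ignores the strata; naming the Cochran-Mantel-Haenszel test as the single primary test is a small improvement that needs no extra patients.

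*Combined protocol and SAP*

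**What the plan says.** Section 9.1 states "Randomization will be stratified by 4 groups", and section 3.1.6 lists them. Two belong to the AL cohort (AML or ambiguous-lineage leukemia on AML therapy, and relapsed ALL). Two belong to the HSCT cohort: "3) those undergoing autologous HSCT; 4) those undergoing allogeneic HSCT". Each cohort is analysed on its own, so each primary analysis has two randomization strata.

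Section 9.3.3 sets the primary comparison: "Within either patient cohort, we will compare the incidence of the bacteremia between the 2 randomized arms using the Chi-square test". Section 9.3.2 uses the same test for power: "The test considered is a 2-sided Chi-square test with alpha level of 0.05". The strata come in afterwards and conditionally: "If within either patient group the data suggest a possible difference in baseline incidence" between the strata, then "we will consider Cochran-Mantel-Haenszel test to examine the association". A stratum-adjusted model is planned without condition: "Logistic regression models will be performed to evaluate the treatment effect on the incidence of bacteremia adjusting for stratification". It is not named as the primary test.

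Section 9.3.4 plans two interim efficacy looks per cohort, at about one-third and two-thirds of the data, with a Lan-DeMets boundary and spending function αt². It does not say which statistic is compared with that boundary.

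**The concern.** The design balances the arms within strata, but the primary test does not use that balance. If bacteremia risk differs between the two strata, the pooled variance in the unstratified chi-square includes a between-stratum part that stratified allocation has already removed from the treatment difference. The test is then slightly conservative and gives up a little power.

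The wording leaves two further questions open. The plan does not say what counts as a suggestion that the strata differ, or whether a CMH test used on that basis would replace or support the chi-square. It also does not say which statistic meets the boundary at the three looks. At stake are a small amount of power in each cohort and a clear answer to which p-value is primary.

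**Working it through.** **Inputs from the plan.** Section 9.3.2 gives AL 133 per arm, 30% vs 15%; HSCT 200 per arm, 20% vs 10%; two-sided α 0.05. Section 2.1 cites post-HSCT bacteremia of 21–34% (autologous) and 21–58% (allogeneic), and notes that some studies found no difference. Section 9.3.2 adds "the recently observed rate of bacteremia in HSCT control arm is 22-25" percent. The documents give neither stratum shares nor stratum-specific AL rates, so those are assumed below.

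**Step 1: reproduce the stated power.** With pooled null variance and no continuity correction, power = Φ{(p₁ − p₂ − 1.96·SE₀)/SE₁}, where SE₀ = √(2p̄(1 − p̄)/n) and SE₁ = √([p₁(1 − p₁) + p₂(1 − p₂)]/n).

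- AL: SE₀ = √(0.34875/133) = 0.05121; SE₁ = √(0.3375/133) = 0.05037; (0.15 − 0.10036)/0.05037 = 0.985, so power is 83.8% (stated 84%).
- HSCT: SE₀ = √(0.255/200) = 0.03571; SE₁ = √(0.25/200) = 0.03536; (0.10 − 0.06998)/0.03536 = 0.849, so power is 80.2% (stated 80%).

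**Step 2: why the chi-square is conservative.** Under the null, with arms balanced inside strata of share wₖ and risk pₖ, the true variance of the difference is proportional to Σwₖpₖ(1 − pₖ). The chi-square uses p̄(1 − p̄), which is larger by Σwₖ(pₖ − p̄)².

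- AL, strata 40% and 20%, equal shares: 0.20 against 0.21, ratio 0.952. The effective cutoff is 1.96/√0.952 = 2.008, so type I error is about 4.5%.
- HSCT, 30% and 10%: 0.15 against 0.16, ratio 0.9375, cutoff 2.024, about 4.3%.
- HSCT, 29% and 21%: 0.1859 against 0.1875, ratio 0.991, cutoff 1.968, about 4.9%.

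**Step 3: simulation.** There were 1,000,000 trials per scenario, with equal arms within strata, a common odds ratio solved to give the stated overall treatment rate, and both tests uncorrected. The αt² boundaries at 1/3, 2/3 and 1 are z = 2.773, 2.347 and 2.062 (nominal p 0.0056, 0.0189 and 0.0392). Each cell is chi-square vs CMH, in percent. Shares are equal unless stated.

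| Scenario (control risk by stratum) | Power, fixed sample | Power, planned looks | Type I error, fixed sample |
|---|---|---|---|
| AL, gap 0 (30/30) | 84.4 vs 84.4 | 82.5 vs 82.5 | – |
| AL, gap 10 (35/25) | 84.7 vs 84.8 | 82.8 vs 83.0 | – |
| AL, gap 20 (40/20) | 85.2 vs 85.9 | 83.3 vs 84.3 | 4.6 vs 5.0 |
| HSCT, gap 0 (20/20) | 81.1 vs 80.7 | 78.9 vs 78.9 | – |
| HSCT, gap 10 (25/15) | 81.2 vs 81.3 | 79.0 vs 79.5 | – |
| HSCT, gap 20 (30/10) | 81.7 vs 82.7 | 79.4 vs 80.9 | 4.4 vs 5.0 |
| HSCT 29/21, risk halved | 90.2 vs 90.2 | 88.7 vs 88.9 | 4.9 vs 5.0 |
| HSCT 34/21 at 30:70, risk halved | 90.2 vs 90.3 | 88.7 vs 89.1 | 4.8 vs 5.0 |
| HSCT 41/21 at 20:80, risk halved | 90.5 vs 90.8 | 88.9 vs 89.6 | 4.6 vs 5.0 |

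Power is lower with the looks because of the looks, not the choice of test. The HSCT gap-10 and gap-20 rows put one stratum below the 21% floor in section 2.1. The last three rows stay inside the cited ranges and the 22–25% control rate.

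**Step 4: does the data-driven trigger inflate error?** Using CMH only when the pooled strata differ, or taking the smaller of the two p-values, gave type I error no higher than about 5.2%. The plain chi-square itself reaches that level in the same scenarios through discreteness. The trigger is not an error-rate problem.

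**Step 5: how often do the tests disagree?** Under the alternative they reach different conclusions in 0.1% of trials at gap 0, 0.3% (AL) and 0.5% (HSCT) at gap 10, and 0.2–0.7% in the three document-range HSCT cases. At an assumed gap of 20 it is 1.0% (AL) and 1.5% (HSCT).

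**The case against.** The strongest reply is that nothing is broken. The chi-square is valid, meets its stated power, is stated without condition in 9.3.3 and is the test powered in 9.3.2, so it is the natural default. The adjusted logistic model ensures that a stratum-adjusted estimate is reported. All of that stands.

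The gain also shrinks when the assumptions are less favourable. With an HSCT control rate of 22%, the lower end of the observed range, and risk halved, chi-square vs CMH is 85.4 vs 85.0 for 23/21 at equal shares and 85.3 vs 85.0 for 26/21 at 20:80 in a fixed sample. At the final-look cutoff these become 82.4 vs 82.4 and 82.3 vs 82.4. At a fixed 0.05 cutoff CMH can lose: 0.4 points for HSCT 20% vs 10% with equal strata, and 1.6 points for AL 60% vs 42.5% (83.4 vs 81.8), where attainable tables lie almost exactly at z = 1.96. At the planned boundaries that AL loss is under 0.1 point (81.1 vs 81.1). A one-patient arm imbalance at gap 20 moves the fixed-sample gain between 0.1 and 1.3 points (AL) and between 0.4 and 1.6 points (HSCT). The gain is therefore comparable in size to discreteness effects.

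Finally, the trial is under way and HSCT control-arm rates have been released, so a change of primary test needs a stated reason. That calls for care in the amendment but does not defeat the change. CMH is already named in 9.3.3, the strata are fixed at randomization, and sample size and α stay as they are.

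**Conclusion.** The point holds, as a modest gain in efficiency and pre-specification and not as a validity error. The primary test does not match the stratified randomization, and the test that does is left to an undefined look at outcome data. At the planned boundaries, CMH gains 1.0 point (AL) and 1.5 points (HSCT) at an assumed 20-point stratum gap. It gains 0.2 to 0.7 points in the three HSCT cases within the cited ranges, and about nothing if the strata do not differ. The size rests on assumed stratum rates and shares, a common odds ratio and near-equal arms within strata. Neither the stated sample sizes nor the 84% and 80% figures need correction.

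**What to change.** In section 9.3.3, make the CMH test stratified by the two randomization strata of each cohort the single primary test, reported with the common odds ratio and its 95% confidence interval. Delete the condition about the data suggesting a difference. Keep the unstratified chi-square, the adjusted logistic model and the Breslow-Day test as supportive, and say that they do not govern the conclusion.

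In section 9.3.4, state that the same CMH statistic is compared with the boundary at both interim looks and at the final analysis. Because the documents do not say whether a look has already been taken, the amendment should give the reason for the change and record the statistic used at any completed look. Extending the change to the binary secondary endpoints is optional.

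The cost is wording in two sections, with no change in sample size or α. With the planned boundaries, the largest power loss found when the strata do not differ was about 0.1 point (AL 40% vs 22.5%, 86.1 vs 86.0). If the sponsor keeps the chi-square, the minimum is one sentence saying that it governs at all three looks and that CMH is supportive. That settles the wording but forgoes the gain.
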